Creating SCTaware Education Once the five sessions are evaluated, the SCT educator will receive additional health literacy- and Adult Learning Theory- based education. The educator will complete an in-depth experiential health literacy training and the online Always Teach-back! Toolkit interactive learning module. From the videos, the Team will create a plain language glossary for the SCT educator to use to reduce medical jargon during the education. The Team will provide specific feedback on strategies to make the education more understandable (e.g., open-ended questions, teach-back method, and Chunk and Check methods).¹⁰ The educator and a health literacy expert will role-play to increase the educators' comfort using these techniques. To ensure the educator consistently uses the health literacy strategies during all sessions, the TEAM will select the two SCTKA items that the educator will consistently use the teach-back method when educating parents about these items. Methods identified by stakeholders and on parents' STNA and EES surveys will be employed to further encourage parental learning. The time required to complete this additional educator training will be recorded. The Team will convert the print visual aids to be appropriate for those with low health literacy and also to be more interactive when they develop the SCTaware ebook that will be accessible on internet-enabled devices. The ebook will also include short videos, image hotspots, and quizzes to promote knowledge retention and to provide parents with a take-home tool to use to promote self-care in the Adapted Health Literacy Conceptual Model (Figure 2) and negotiate conversations about SCT with their family. The visual aids and ebook will be revised until they achieve pre-determined SAM, CDCCI, and PEMAT scores.

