SCT testing Barriers that prevent parents from obtaining SCT testing must be identified in order to increase SCT status awareness. Unresolved decisional conflict about whether or not to obtain SCT testing is a potential barrier, since the test results can have high-stakes for individuals who are identified as having SCT (e.g., being at risk for having a child with SCD). Decisional conflict is the psychological distress experienced when making a choice and it can lead to delayed and ineffective decision-making. Because decisional conflict can occur when individuals are uninformed about their options, effective education has the potential to reduce conflict and increase decision satisfaction. We will, therefore, use the Decisional Conflict Scale (DCS) to explore if parents experience decisional conflict about whether or not to obtain SCT testing and if SCTaware reduces this conflict (*Aim 2b*). Another potential barrier is that most parents of these children are African American and may not have access to a consistent provider who can order this testing.³⁸ To address this potential barrier, SCT testing will be available on-site, but not paid for, to participants after the educational program. SCT testing includes a CBC and a hemoglobin electrophoresis, and a paper order, signed by [name] (the PI and hematologist), will be provided to participants who wish to obtain this testing. Parents will be provided contact information for common insurance companies to determine if the testing will be covered but also informed of the estimated cost if not covered (~\$250). Finally, parents will be asked to report if they have other testing barriers (e.g., needle phobia, already aware of SCT status). [name] will review and interpret all test results and the SCT results will be mailed to tested parents. The research coordinator, using the teach-back method, will confirm test result receipt when parents are contacted to complete follow-up surveys.

Interim analyses will confirm that SCTaware does not result in more parents to have lower knowledge at 6 months. Several random sessions during Phase II will also be recorded and reviewed to confirm SCTaware education fidelity and that the teach-back method was used for the critical items, or if educator re-training is required.

6. Measures

Phase I:

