Demographic Survey Participants will self-report their age, SCT status, gender, race, ethnicity, primary language spoken, employment status, household income, and highest education level achieved.

NVS Participants will complete the NVS health literacy tool prior to their SCT education session. The NVS can be completed in less than three minutes and is highly sensitive for detecting adults with low health literacy.¹¹ Scores range from 0-6, and scores <4 will be considered low.

SCTKA Participants will complete the 8-item SCTKA (Table 2) before and after they receive education. This tool was used to quickly assess SCT knowledge during our preliminary study⁵ and to be understandable by those with low literacy levels. It was pilot tested in parents of children with SCT to ensure readability and seven of the items were previously published.¹² Scores <75% correct will be considered low.

STNA The SCTaware program in Phase II will make on-site SCT testing convenient to parents. To identify parents' testing needs and potential methods to use during SCTaware to promote parental learning and testing, parents will complete the STNA. It will ask parents about their knowledge of their SCT status and their intentions for obtaining SCT testing and it will be developed using the results of a qualitative study of pregnant women who identified the factors they found important when deciding whether or not to obtain SCT testing and will be pilot tested for readability on parents who come for standard in-person education and revised based on their feedback.¹³

EES Participants will complete a modified version of the education satisfaction survey that was used in the preliminary study.⁵ The EES will gauge parents' reported readiness and responsibility for learning about SCT, if the education they received met their learning goals, if they have the self-efficacy to apply their knowledge to make informed reproductive health decisions, and if they have (or plan to) notify family members or their communities about SCT and their SCT status. Participants will provide open-ended feedback and offer methods to improve and/or broaden the SCTaware program to increase SCT knowledge and awareness.

Phase II:

Demographic, NVS, SCTKA, STNA, and EES Same as in Phase I.

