7. Survey Completion- A research coordinator will read all survey items to participants and record their responses electronically. This format will be used because participants are only required to have functional verbal English and the NVS was validated using an interview format. This will also ensure that the method of survey completion is consistent in Phase II because the follow up surveys at 1 and 6 months will be over the telephone.

8. Study Compensation

Phase I: Participants will receive \$25 for completing Phase I.

Phase II: Participants will receive \$25, \$5, and \$10 for completing the initial, 1-month, and 6-month surveys, respectively.

9. Safety

a. Privacy

Participants' data will be de-identified to minimize the risk that participants' survey responses will be intercepted by a third party. The assessments will be completed electronically and stored in Redcap.

b. Data Storage

The survey results will be stored on a research drive that is maintained behind NCH secure firewall. The research data will be retained for 7 years after publication of the data, in accordance with standard research methods. After this time all collected data will be destroyed.

10. Data Management and Statistical Analysis

a. Data Monitoring

Study data will be collected, downloaded, and stored on RedCap. This database will only contain de-identified patient adherence data and will be linked by study ID number.

b. Statistical Methods and Analysis

Phase I: SCTaware will be deemed feasible if educator training and the time to deliver SCTaware can be delivered within the context of the current SCT program at NCH.

Phase II: During our preliminary study, ~40% of parents had high SCT knowledge prior to receiving education and 90% percent of parents achieved high SCT knowledge immediately after they received the current standard education program,⁵ however, it was unclear if this knowledge was sustained at 6 months because few parents completed the 6-month SCTKA. To determine if significantly more parents who receive SCTaware education have high SCT knowledge 6 months after receiving the education compared to baseline (Aim 1b, the primary aim for Phase II of the study), we will enroll 128 (n=98 evaluable) parents on Phase II of the study. This sample size was calculated using a two-sided, McNemar's test and has 80% power, with a 5% alpha, and assumes 30% attrition (Aim 1b).

Study Design	Knowledge Level at 6-month after SCTaware		

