	Proportion with High Knowledge	Proportion with Low Knowledge	
Knowledge Level pre-SCTaware Education	Proportion with High Knowledge	30%	15%
	Proportion with Low Knowledge	35%	20%

Similar to our preliminary results, this example assumes that 45% of participants will have high SCT knowledge before receiving SCTaware and 65% will have high SCT knowledge 6 months after receiving SCTaware education. Therefore, a sample of 98 evaluable participants will have 80% power to detect an odds ratio of 2.33 when the proportion of discordant pre and post-SCTaware pairs is 0.5.

11. Quality Assurance

a. Training of research Staff

Prior to enrollment, the research team will meet to review all protocol procedures, including screening, enrollment, and survey administration. The PI will insure that all research staff who consent, enroll, and complete study follow up assessments are adequately trained. The research team will meet at least monthly during active enrollment and to discuss any potential problems and then at least bi-monthly while participants are still actively participating in the study.

12. Dissemination of Results and Publication

a. Planned Journal for Submission

Phase I: J Genet Counseling

Phase II: Pediatrics

b. Authorship

[name], [name], [name], [name], [name], [name]

13. Timeline

Dates	Phase
April 2019-October 2019	Phase I
October 2019-April 2021	Phase II

14. Anticipated Problems and Solutions

1. Meeting recruitment goals is a challenge of all studies, however, this study will use the same strategy that successfully enrolled 91% of eligible parents in <12 months. To further encourage participation, this study will also include participation incentives and we have also expanded the eligibility criteria to include parents with functional verbal English (do not request interpreter services).

2. Recruitment bias is possible, since only parents who present for in-person education will be included. Once SCTaware is developed, however, adapting the program for electronic delivery may increase the number of parents who can receive this strategy.

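### Does mandated teach-back on two of the eight SCTKA items leave the 6-month knowledge result unsound without a separate analysis of the other six?

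*Combined protocol and SAP*

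**What the plan says.** Section 6 (Measures, SCTKA) defines the instrument and its cut-off: "Participants will complete the 8-item SCTKA" and "Scores <75% correct will be considered low". Six of eight is exactly 75%, so high knowledge means at least 6 correct. Section 6 carries the SCTKA unchanged into Phase II.

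Section 5.f, Phase I (Creating SCTaware Education) provides that "the TEAM will select the two SCTKA items that the educator will consistently use the teach-back method when educating parents about these items". The reason given there is consistent use of the health literacy strategies in every session. The same paragraph lists teach-back among general techniques for the whole session, beside open-ended questions and Chunk and Check. In section 5.f, Phase II, some randomly chosen sessions are recorded and reviewed "to confirm SCTaware education fidelity and that the teach-back method was used for the critical items". That sentence gives no number, but the two selected items are the natural reading.

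Section 10.b makes Aim 1b the primary aim of Phase II: high knowledge at 6 months compared with baseline. It specifies McNemar's test for 98 evaluable parents. No item-level or six-item analysis at 6 months is described. Item-level review of the SCTKA appears only in Phase I, to revise the program.

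**The concern.** A quarter of the score receives an enforced and monitored technique, and the cut-off allows exactly two wrong answers. A parent with 4 or 5 correct at baseline could become high by gaining only the two teach-back items. With one group and one binary outcome, the planned test cannot tell that from wider learning.

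The rationale (section 1.2) wants parents to know their own risk and to inform their children later. If the gain were confined to two items, calling SCTaware effective education would say more than the data show. The plan's own uncertainty about retention adds to the worry: for the existing program, "it was unclear if this knowledge was sustained at 6 months".

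**Working it through.** **The plan's own figure.** Inputs from section 10.b: "this example assumes that 45% of participants will have high SCT knowledge before receiving SCTaware", 65% at 6 months, discordant cells 35% and 15%, two-sided 5% alpha, 80% power.

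- Odds ratio: 0.35/0.15 = 2.33, as stated.
- Discordant proportion: 0.35 + 0.15 = 0.50. Difference: 0.35 − 0.15 = 0.20.
- n = (1.960 + 0.842)² × 0.50/0.20² = 98.1. The unconditional form gives 95.7. The stated 98 reproduces.

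Nothing in this calculation refers to individual items. It sizes a comparison of the total-score category, which is what Aim 1b names.

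**How far two items alone could move the endpoint.** The documents give no item difficulties, no correlation between items and no 6-month retention, so what follows is a range under assumptions. Leave six items at their baseline probability p and let each of the two be correct with probability r at 6 months. Let X be the number correct among the six. Then

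P(high) = P(X=6) + P(X=5)·[1 − (1−r)²] + P(X=4)·r².

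For eight equally hard, independent items, 45% high at baseline requires p = 0.659. This gives P(X=6) = 0.082, P(X=5) = 0.255 and P(X=4) = 0.329.

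- r = 0.90: 0.082 + 0.255 × 0.99 + 0.329 × 0.81 = 0.601
- r = 0.95: 0.082 + 0.255 × 0.9975 + 0.329 × 0.9025 = 0.633
- r = 1.00: 0.082 + 0.255 + 0.329 = 0.666

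The table allows parents to differ in ability (SD on the logit scale; 0 means independent items). It shows the change from 45% in percentage points.

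| Two items at baseline | r | SD 0 | SD 1 | SD 1.5 |
|---|---|---|---|---|
| 80% correct | 0.90 / 0.95 | +6.0 / +9.1 | +1.8 / +3.9 | +0.2 / +1.8 |
| As hard as the rest | 0.75 / 0.80 | +5.6 / +8.7 | +3.0 / +5.1 | +2.0 / +3.7 |
| As hard as the rest | 0.90 / 0.95 | +15.1 / +18.3 | +9.5 / +11.7 | +7.1 / +8.8 |
| 40% correct | 0.90 / 0.95 | +31.8 / +34.8 | +22.3 / +24.4 | +17.5 / +19.2 |

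SD 0 fits the plan's table best. Independence of the two time points implies 0.45 × 0.35 + 0.55 × 0.65 = 0.515 discordant, against the plan's 0.50. SD 1 and 1.5 imply about 0.32 and 0.26. In the table, the planned +20 is reached only when the two items start much harder than the rest. At equal difficulty it takes every parent answering both correctly (+21.6). Section 5.f does not say how the two are chosen, so neither the hard nor the easy case can be excluded.

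**Is no gain on six taught items plausible?** Section 10.b reports about 40% high before the current education and 90% immediately after, without a two-item rule. Start the same model (SD 0) from 40%, hold six items fixed and make the other two perfect. The share reaches 62% if all are equally hard, 78% if the two start at 40% correct and 84% if they start at 30%. All fall short of 90%, so under these assumptions the existing session already teaches more than two items. This is an immediate result and says nothing about 6 months.

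**Is two versus six a clean contrast?** It is not. In Phase I the team reviews wherever the session failed to produce a correct SCTKA answer, with no limit to two items. SCTaware then adds educator training, a plain-language glossary and an ebook with quizzes for the whole content. Teach-back is not barred for the other six.

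**The case for a change.** The best case for acting is that Aim 1 is about effective education, that the binary total cannot show breadth, and that recording the two items in advance would prevent a later choice of items to suit the result. The six-item change would also be informative. If a rise from 45% to 65% were spread evenly, the six items would gain 0.48 to 0.82 items on average. With a paired SD of 1.42 to 1.58, the 95% half-width at n = 98 is about 2 × 1.42/√98 = 0.29 to 2 × 1.58/√98 = 0.32. A broad gain could be told from none.

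That arithmetic stands, and so does the observation that no such analysis is planned. It does not follow that the plan is wrong. The six-item change would show where scores moved, not why. In a single group given the same test four times, repeat testing could raise the six items. Baseline difficulty or a ceiling could make two items move differently from six without any effect of teach-back. Correct answers on the two items are also real knowledge gained from the intervention, and a parent who has both right still needs four of the other six to count as high.

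**Conclusion.** The concern does not hold. The facts behind it are correct, but the endpoint, the test and the sample size all address the aim as written: whether the share of parents at 6 of 8 or better rises. Teach-back on two items is a component of the program under study, and the plan makes no statement about how the gain is distributed over items.

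The possible contribution of the two items alone runs from about 0 to +35 points. It rests on assumed difficulties (40% to 80% correct at baseline), assumed retention (90 to 95%) and the strong assumption of no lasting gain on the other six. That range does not show a defect. The primary result would be valid at either end.

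Item-level results may be worth describing in the report, and a claim there of uniform learning across items would need them. That is a matter of preference in reporting. The point lapses altogether if SCTaware proves infeasible and the current education is tested in Phase II, as section 5.f (Pilot Testing SCTaware Education) allows.

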1.3. Aims

Aim 1. Develop an effective SCT education program for parents of infants with SCT identified by NBS.

- 1a. Determine the feasibility of implementing a SCT education program (SCTaware) that is appropriate for all parents, including those with low baseline knowledge and low health literacy. (Phase I)
- 1b. Determine if significantly more parents who receive SCTaware education have high SCT knowledge 6 months after receiving the education compared to baseline.

Hypotheses: SCTaware will require limited additional resources to implement compared to Ohio's current program and it will result in significantly more parents to have high SCT knowledge.

Approach: A comprehensive team will develop SCTaware education through iterative review and revision of the current in-person program. The time required to train the educator and to administer SCTaware to parents will be recorded. SCTaware will be feasible if educator training can be completed during administrative time and if SCTaware can be provided to parents within Ohio's existing appointment schedule (Phase I). The SCT Knowledge Assessment will measure parents' knowledge before, after, and 6 months post-SCTaware (Phase II).

Aim 2. Determine the barriers that prevent parents of infants with SCT from getting SCT testing.

- 2a. Determine the percentage of parents who obtain on-site SCT testing at time of SCTaware education. (Phase II)
- 2b. Determine the range of decisional conflict that parents may experience regarding SCT testing before and after receiving SCTaware education. (Phase II)

Hypotheses: Making on-site testing available will result in $\geq 50\%$ of parents who are educated to obtain testing. Parents will have decisional conflict about whether to obtain testing that will be reduced with SCTaware education.

Approach: Parents will self-report their SCT status before receiving education. The number of parents that obtain on-site testing will be recorded. We will use the Decisional Conflict Scale to measure parents' uncertainty about obtaining SCT testing before and after education. Parents who do not obtain testing will be asked to report their other testing barriers (e.g., cost, needle phobia, other).

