Pilot Testing SCTaware Education Two new parents will be recruited to pilot test the SCTaware education, to have their SCTaware session video-taped and to complete the associated surveys, but additional parents will be recruited, if needed, so that at least one parent with low health literacy and baseline SCT knowledge pilot test the new program. The Team will the revise the SCTaware program again after reviewing their videos and surveys and pilot test the revised SCTaware program on two additional parents (at least one with low health literacy and baseline SCT knowledge). This process will continue iteratively until the Team agrees that the SCTaware program is finalized. The time required to deliver the SCTaware education during pilot testing will

be recorded. If it is not feasible to deliver SCTaware (i.e. SCTaware education cannot be delivered within the context of the current in-person SCT program), the current in-person SCT education will be tested in Phase II.

Parent stakeholders The NCH hemoglobinopathy team will help the Research Team identify the parent stakeholder of a child with SCT who has previously received the standard SCT education and the parent of a child with SCD who is currently followed by the NCH Hemoglobinopathy Team. These stakeholders will be compensated \$1000 each for their time to review the sessions and to provide their feedback, insights, and lived-experience that will inform the SCTAware education.

Phase II:

Study Design Phase II will be a six-month prospective study.

Recruitment Using the same recruitment strategy as in Phase I, we will recruit 128 parents.

Study Procedures Prior to receiving SCTaware, participants will self-report their SCT status and complete the demographic survey, SCTKA, State Trait Anxiety Index for Adults (STAID), and Decisional Conflict Scales (DCS).

Surveys	Before	After	Follow Up #1	Follow Up #2
	Day 1	Day 1	1 mo	≥6 mo
Demographics	x			
Self-reported SCT status	x		x	x
NVS	x			
SCTKA	x	x	x	x
DCS	x	x	x	
STNA		x		
STAID	x	x		
EES		x	x	x
ebook Survey			x	x

Table 2. Phase II Study Measures

SCTaware sessions will be timed. Participants will complete the DCS, EES, STNA, SCTKA, STAID immediately after their session and a research coordinator will contact parents by telephone one month and ≥6 months after their session to complete additional surveys (Table 2).

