Self-Reported SCT Status and Obtaining SCT testing Parents will self-report their SCT status multiple times during the study to determine if self-reported SCT status is reliable and accurate and impacts their decision to obtain testing. The percentage of parents who obtain on-site testing will be recorded to determine if on-site testing increases SCT status awareness and if tested parents can accurately recall their status ≥6 months after they were tested.

STAID (short form) Qualitative studies suggest that SCT education has the potential to reduce parental anxiety.⁶ The STAID short form is a 20-item sensitive and reliable measure of state anxiety and will be used to quantify parents' anxiety before and after receiving SCTaware education (Table 3).^{14,15}

DCS Participants will complete the 16-item validated tool to determine if decisional uncertainty is a SCT testing barrier for parents and if SCTaware increases parents' perception that they made an informed decision about whether to obtain testing. DCS has predictive validity over a range of decisions, and in studies of decision-supporting interventions, effect sizes ranged from 0.4-1.2.¹³⁻¹⁵

ebook Survey While most parents will have an electronic device, the non-interactive ebook content will be printed. Parents will be asked to report the type of device(s) they have since readability may differ by device, and to provide feedback on the content and format. They will also be asked to report how often they accessed the ebook since their in-person education to support their learning or to share information about SCT with their families and communities.

Time to Deliver SCTaware Education and Notifications Although health literacy-based methods can marginally increase the time to deliver information, in return, more learners may comprehend the information presented.¹⁶ We will compare the time to provide SCTaware education (Phase II) to Ohio's current in-person SCT education (Phase I). We anticipate that familiarity with SCTaware will reduce delivery time. The time to deliver parents' test results will also be recorded to determine if this testing can be included within the SCTaware program.

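### Could going over the test result on the follow-up calls prompt tested parents' self-reported SCT status?

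*Combined protocol and SAP*

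**What the plan says.** In the protocol, Section 5f (Phase II, SCT testing) says that "the SCT results will be mailed to tested parents" and continues: "The research coordinator, using the teach-back method, will confirm test result receipt when parents are contacted to complete follow-up surveys".

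The contacts are defined under Phase II Study Procedures: "a research coordinator will contact parents by telephone one month and ≥6 months after their session to complete additional surveys". Table 2 marks self-reported SCT status on Day 1 before education and at both follow-ups. Section 7 fixes who asks and how: "A research coordinator will read all survey items to participants and record their responses electronically", and "the follow up surveys at 1 and 6 months will be over the telephone".

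Section 6 (Self-Reported SCT Status and Obtaining SCT testing) gives the purpose of repeating the question: "to determine if self-reported SCT status is reliable and accurate and impacts their decision to obtain testing". It also wants to learn "if tested parents can accurately recall their status ≥6 months after they were tested".

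No section states whether the status question precedes or follows the teach-back, or whether teach-back is done at the 1-month call only or at both.

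**The concern.** The coordinator role that goes over the result also records the parent's answer about status, on the same telephone call. Teach-back has the parent restate information and corrects what is wrong. If it came before the status question, a parent who had forgotten or misunderstood the result could be put right just before the answer was recorded. That answer would then count as accurate recall.

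The error could go only one way, upward, and would affect only tested parents. It would therefore inflate recall at 6 months or later and would distort any comparison of follow-up accuracy between tested and untested parents. An unprompted answer that was never taken cannot be reconstructed in analysis. If the order is not recorded, the prompted answers cannot be picked out either.

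**Working it through.** **What has to happen for bias to arise.** The plan gives no recall rate or order to recompute, so the first check is textual. Same-call bias in recall at 6 months or later needs all of the following:

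1. Teach-back takes place on that call. Section 5f speaks of confirming receipt of a mailed result, which is naturally done once, at the first contact. Its plural reference to surveys allows both calls but does not require both.
2. Teach-back comes before the status question. No section says so. Among the measures Table 2 marks at the follow-ups, self-reported status is listed first. The table does not fix a sequence, but it does not point to teach-back first.
3. The coordinator states, cues or corrects the result before recording status. Teach-back starts from the parent's own words, so a parent who states the result correctly before any cue has shown recall.
4. The corrected answer, not the first one, is recorded. No section describes this.

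**What is out of reach of the calls.** The Day 1 self-report is taken before education, and on-site testing is offered after it. Comparing that report with the test result gives a check of self-report accuracy that no later call can affect. The same report is the one that can bear on the decision to be tested. The primary endpoint is high knowledge on the SCTKA at 6 months against baseline and does not use this item.

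**Number of parents involved (assumed).** Section 1.3 hypothesises that at least 50% "of parents who are educated to obtain testing". Take exactly 50%, and attrition unrelated to testing. Section 10b gives 128 enrolled, 98 evaluable and 30% attrition.

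- Tested: 0.5 × 128 = 64.
- Reached at 6 months or later: 0.5 × 0.70 × 128 = 44.8, about 45; or 0.5 × 98 = 49.

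**Size of the bias (assumed).** Let r be unprompted recall, q the share of calls with teach-back first, and c the share of wrong answers that prompting turns into recorded right ones. Recorded accuracy is r + q·c·(1 − r), so the bias is q·c·(1 − r). The 95% half-width is 1.96·√(r(1 − r)/n). All entries are percentage points.

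| | r = 0.6 | r = 0.7 | r = 0.8 | r = 0.9 |
|---|---|---|---|---|
| Bias, q = 1, c = 1 | 40 | 30 | 20 | 10 |
| Bias, q = 0.5, c = 1 | 20 | 15 | 10 | 5 |
| Bias, q = 0.5, c = 0.5 | 10 | 7.5 | 5 | 2.5 |
| Bias, q = 0 | 0 | 0 | 0 | 0 |
| Half-width, n = 45 | 14.3 | 13.4 | 11.7 | 8.8 |
| Half-width, n = 49 | 13.7 | 12.8 | 11.2 | 8.4 |

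The top row needs teach-back first on every call and every wrong answer corrected. With half and half, the bias is below the sampling half-width at every r shown. For recall at 6 months or later, q is 0 if status is asked first, and also if teach-back is done only at 1 month.

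**The case for a change.** The best case for a change is that the gap is real and closing it is nearly free. The two activities do share the calls, the protocol is silent on their order, and any bias inflates a measure that Section 6 names as a purpose. With teach-back first on every call and every error corrected, the bias exceeds the sampling half-width at each recall rate in the table. Even if teach-back were confined to 1 month, the 1-month status answer could still be prompted, and the later answer would follow an earlier reinforcement.

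Much of that stands. The silence is there, the direction of any bias is right, and asking status first is plainly the better practice. What does not stand is the step from silence to a flaw. Item order in a telephone interview is ordinarily set in the script or data form, and an order may already exist there. Section 11 has the team review survey administration before enrolment and has the principal investigator ensure that staff who do follow-up assessments are trained. That fixes no order, but it is where one would be settled. The large figures need every assumption at its worst. Reinforcement from a 1-month teach-back is part of the planned notification; it affects how later recall is described, not whether the answer is valid.

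**Conclusion.** No change to the plan is needed. The omission is a detail of call conduct that a coordinator following ordinary interview practice fills by asking status before discussing the result. The plan can be carried out exactly as written without producing a wrong figure.

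If the order were reversed, follow-up accuracy among roughly 45 to 49 tested parents would be too high by an unknown amount. With r = 0.8, that is 5 points under the half-and-half assumption and 20 at most. These sizes rest on assumed recall, order and correction rates, and on 50% of parents being tested; the documents supply only the 50% hypothesis, the enrolment and evaluable numbers and the attrition. Section 10b attaches no test, threshold or power to recall.

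When results are reported, recall at 6 months or later is best read as recall after a mailed result and any earlier teach-back.
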